The use of an isoprenaline infusion to induce an episode of atrial fibrillation has become part of clinical practice without the rigorous scientific evaluation usually considered necessary for adoption.

Animal studies have demonstrated a number of mechanisms by which this drug might precipitate atrial fibrillation if the substrate for that arrhythmia is present. However, there is good evidence to suggest that a sympathomimetic alone might not be sufficient to induce atrial fibrillation. Proposed instead is that chance fluctuation in vagal tone during administration of the drug creates the autonomic milieu required.

Although numerous studies have utilised an isoprenaline infusion in the context of ablation of atrial fibrillation seemingly to good effect, without a placebo control it is difficult to interpret the relative effect in a setting where the patient's own autonomic nervous system is likely to be stimulated. It is also impossible to build an understanding of the meaning of inducibility by isoprenaline without first definitively establishing the effect.

Administration of an isoprenaline infusion is safe, however the additional ablation that it is being used to guide carries risk including of life threatening perforation. It is imperative that there is a clear understanding of the magnitude of effect of an isoprenaline infusion in this context so that clinicians can use this potentially beneficial ablation protocol with confidence whilst keeping patient safety paramount.

Our research proposal will provide an answer to the question of "Can an infusion of isoprenaline be used to induce an episode of atrial fibrillation?" We will answer this question using a double blind, placebo controlled trial and will answer it for subjects at very high risk for an episode of atrial fibrillation, those at intermediate risk and in those with a low risk separately.

The second important question this research will answer; "Is the response to an isoprenaline infusion consistent in the same person on different occasions?" This has huge importance if isoprenaline inducibility is to be used to guide therapy. To answer this question our protocol uses open label administration of an isoprenaline infusion to subjects on two separate occasions and compares the results. This will be performed for a group with a history of previous paroxysmal atrial fibrillation.

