The protocol for this study will answer a number of subsidiary questions to further improve the scientific quality of the evidence regarding this use for Isoprenaline. We will collect observational data as part of this protocol which will directly inform the design of planned future studies in this area.

Future Application for Findings and Further Investigation

This project represents a foundation to future studies investigating the clinical utility of an isoprenaline infusion. If, backed by the sound, scientific evidence that our project will deliver, isoprenaline infusion is validated as able to induce atrial fibrillation, we intend to investigate its potential ability to identify patients with substrate for atrial fibrillation, especially in subjects where that arrhythmia has not before been seen clinically.

The group where this use is potentially most interesting is in assessment of those attending for common type atrial flutter ablation in whom atrial fibrillation had not before been documented. Meta analysis³ suggests as many as 25% of these patients will go on to get atrial fibrillation in the 12 months after their ablation. We propose that non-inducibility of atrial fibrillation by high dose isoprenaline infusion following a cavotricuspid isthmus ablation (as treatment for atrial flutter) might predict a low risk group for clinical atrial fibrillation. This might then be able to be used to inform anticoagulation or further treatment.

We plan to secure national level funding for a 350 patient, cohort study with the aim of commencing recruitment in 2015/6. If this technique allows us to characterise a very high or very low risk population, it could quickly be applied to clinical decision making on issues such as preventative medication, anticoagulation and treatment timing for atrial fibrillation, potentially reducing stroke risk in a substantial cohort of patients. We feel this offers a clear route to future patient benefit.

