- An occurrence of an episode of atrial fibrillation lasting greater than 30 seconds and documented on either 12 lead ECG or on ambulatory ECG monitoring in the 12 months following an ablation procedure
- Time in days from ablation procedure to the occurrence of an episode of atrial fibrillation lasting greater than 30 seconds and documented on either 12 lead ECG or on ambulatory ECG monitoring
- An occurrence of an episode of atrial fibrillation lasting less than 30 seconds and documented on either 12 lead ECG or on ambulatory ECG monitoring in the 12 months following an ablation procedure
- Recurrence of the ablated arrhythmia
- Occurrence of a novel arrhythmia other than atrial fibrillation
- Discontinuation of Anticoagulation
- Stroke
- Myocardial Infarction
- Hospitalisation for heart failure
- Hospitalisation for bleeding episode
- Hospitalisation for any cause
- CV Death
- Death from any cause
- Change in quality of life questionnaire

Subject Identification and Recruitment

Subject Groups

The study is organised with subjects divided into specific groups which will be analysed separately. These groups include;

- 1. Paroxysmal Atrial Fibrillation Group
- 2. Supraventricular Tachycardia (SVT) Ablation Group
- 3. Atrial Flutter Ablation Group
- 4. Pulmonary Vein Isolation Group

The participant's past history of abnormal heart rhythms will be used to indicate their risk for developing atrial fibrillation based on previous epidemiological studies. Those with known clinical paroxysmal atrial fibrillation will represent the highest risk group, those undergoing ablation for an SVT will be considered low risk and those undergoing ablation for atrial flutter will form an intermediate risk group.

Potential participants will be identified as being possible study candidates at the time of clinical review as part of their usual care. Clinicians or other healthcare professionals performing such a clinical review will identify the subject as a potential candidate for recruitment, will mention the study to the potential participant and highlight their case to the study team for so that they may approach that person to recruit them. For participants in Part B, it is anticipated that this will be the review from which they are listed for an ablation procedure. The clinical team will also review the case notes for patients already listed for an ablation procedure in their centre and potential candidates identified in this manner will be approached.

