- Participants must have a pattern of symptoms and investigation results consistent with a diagnosis of paroxysmal atrial fibrillation

Group 2 – SVT Ablation Group

- Participants must have a history of arrhythmia with documented regular, narrow complex tachycardia available on either 12 lead ECG or ambulatory ECG monitor recording
- Participants must be listed to undergo an Electrophysiology study with a view to performing an ablation procedure
- Participants must go on to have an ablation procedure for either Atrio-Ventricular Re-entrant Tachycardia (AVRT) or Atrio-Ventricular Nodal Re-entrant Tachycardia (AVNRT) with a defined procedural endpoint

Group 3 – Atrial Flutter Ablation Group

- Participants must have a history of arrhythmia with 12 lead ECG documentation fulfilling prespecified criteria for diagnosis of common type (cavotricuspid isthmus dependent) atrial flutter
- Participants must be listed to undergo a cavotricuspid isthmus ablation for common type atrial flutter
- Participants must go on to have only a cavotricuspid isthmus ablation for common type atrial flutter
- Sustained bi-directional cavotricuspid isthmus block must have been demonstrated as the endpoint for the ablation procedure

Group 4 – Pulmonary Vein Isolation Group

- Participants must have a history of arrhythmia with 12 lead ECG or ambulatory ECG monitoring recordings documenting a diagnosis of atrial fibrillation
- Participants must be listed to undergo an ablation procedure for atrial fibrillation with the intent of the attending physician to perform pulmonary vein isolation alone as an ablation strategy
- Participants must be in sinus rhythm at the time that they enter the Cardiac Electrophysiology Laboratory for their ablation procedure.
- Participants must have an ablation procedure for atrial fibrillation and this must have involved only ablation to achieve pulmonary vein isolation
- Pulmonary vein isolation must have been demonstrated as the endpoint for the ablation procedure

Exclusion Criteria

All Participants in All Groups

- Allergy to Isoprenaline
- Any treatment with Amiodarone in the 3 months prior to ablation procedure
- Hypertrophic cardiomyopathy
- Suspected acute myocarditis
- Uncorrected, severe valvulopathy graded by transthoracic echocardiographic parameters
- An Acute Coronary Syndrome within the last 6 months
- Recent (within the last 6 months) or scheduled coronary revascularisation

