- Ongoing angina symptoms without investigations demonstrating the absence of myocardial ischaemia
- Left ventricular ejection fraction measured at <30%
- Symptoms of decompensated heart failure syndrome in the last 3 months
- Severe obstructive lung disease
- Pregnancy at the time of enrolment or a desire to become pregnant during the study period
- Women who are breastfeeding
- Reduced life expectancy not associated with cardiovascular disease (less than 1 year)
- Unable to provide informed consent

Group 1 – Paroxysmal Atrial Fibrillation Group

- Any past history of episode of persistent atrial fibrillation at the time of enrolment to the study
- Treatment with any antiarrhythmic agent within six half-lives of that agent from before an administration of the study drug infusion

Group 2 – SVT Ablation Group

- Any past history of atrial fibrillation documented on 12 lead ECG or ambulatory ECG monitor
- Any past history of atrial flutter documented on 12 lead ECG or ambulatory ECG monitor
- Characterisation of SVT as any arrhythmia other than ANRT or AVNRT
- Treatment with any antiarrhythmic agent within six half-lives of that agent from the ablation procedure (including intra-procedural use) with the exception of isoprenaline and adenosine

Group 3 – Atrial Flutter Ablation Group

- Characterisation of arrhythmia as any arrhythmia other than cavo-tricuspid isthmus dependent atrial flutter at the time of ablation
- Treatment with any antiarrhythmic agent within six half-lives of that agent from the ablation procedure (including intra-procedural use) with the exception of isoprenaline and adenosine

Group 4 – Pulmonary Vein Isolation Group

- Requirement for a more extensive ablation strategy than pulmonary vein isolation alone
- Intra-procedural treatment with any antiarrhythmic agent with the exception of isoprenaline and adenosine
- Treatment with any antiarrhythmic agent in the days before the ablation within six half-lives of that agent from the ablation procedure

Participant Information

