At this enrolment visit the investigators will take baseline demographics and medical information and will perform some non-invasive measurements. Baseline demographics will include age, sex, marital status, occupation and ethnic group. Baseline medical information will include diagnosis for which patient is undergoing ablation procedure, duration of that diagnosis, duration of symptoms relating to diagnosis, number of episodes of symptoms in the month prior, NYHA class, CHADS₂ score, CHA₂DS₂ VASc score, HAS BLED score, Framingham risk of atrial fibrillation score, past cardiac history and the presence of any co-morbidities. All available previous 12 lead ECG and ambulatory ECG recordings will be reviewed and previous arrhythmia episodes will be documented. Usual alcohol consumption, smoking status and exercise / activity history will also be recorded. Measurements taken of basic physiological observations will include pulse rate and rhythm, blood pressure, oxygen saturations, weight in kilograms and height in metres. At this first visit, blood pressure from both arms will be recorded. All subjects will undergo 12 lead ECG recording. Where the optional consent is provided, blood samples will be taken. Blood will be taken with the intention of storing it for future analysis. This analysis will not have been determined at the time of sampling and patients will be consented for this. The analysis may include genetic testing.

Subjects will complete a quality of life questionnaire which will be a modified combined version of the RAND 36 item health survey (a measure of general health status) and the Symptom Checklist— Frequency and Severity Scale (an instrument specific for cardiac arrhythmias).

At the end of the enrolment visit, each participant will be fitted with a Novacor R-Test ambulatory ECG monitor which, on this and each occasion they are required to wear one during the study, they will wear continuously for a period of 7 days. Where available, each subject will be offered an addressed, pre-paid envelope in which to return the device.

• Part B - Visit 2 – Ablation Procedure

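### Experiment 3 is to give the intermediate-risk answer, but the flutter group may include patients with known AF, whom the protocol itself classes as highest risk

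*Protocol*

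**What the plan says.** Under Justification for Research, the protocol undertakes to answer its main question for subjects at very high risk, "those at intermediate risk and in those with a low risk separately".

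Under Subject Identification and Recruitment, Subject Groups, the participant's rhythm history is to indicate risk. "Those with known clinical paroxysmal atrial fibrillation will represent the highest risk group", SVT ablation patients are low risk, and "those undergoing ablation for atrial flutter will form an intermediate risk group".

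The Exclusion Criteria for Group 2 (SVT) remove "Any past history of atrial fibrillation documented on 12 lead ECG or ambulatory ECG monitor". Group 3 (flutter) has no matching line. Its rhythm exclusion is "Characterisation of arrhythmia as any arrhythmia other than cavo-tricuspid isthmus dependent atrial flutter at the time of ablation", and its inclusion criteria add that "Participants must go on to have only a cavotricuspid isthmus ablation for common type atrial flutter".

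Experiment 3, under Study Objectives, is a single isoprenaline-versus-placebo comparison after flutter ablation, with 35 per arm. Study Procedure - Protocol Part B gives 1:1 allocation within each participant group and states no stratification by AF history.

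Under Future Application for Findings, the group named as most interesting for later use is "those attending for common type atrial flutter ablation in whom atrial fibrillation had not before been documented". At Part B, Visit 1, "All available previous 12 lead ECG and ambulatory ECG recordings will be reviewed and previous arrhythmia episodes will be documented".

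**The concern.** The risk classes are meant to be distinct, and AF history is what separates the top class from the others. Group 3 lets that history in. A patient with common flutter and known paroxysmal AF fits two class definitions, and the protocol does not say which takes precedence. Such a patient enters Experiment 3 and is read as intermediate risk.

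What is at stake is attribution. If patients with prior AF are induced more readily than those without, the pooled rate describes neither. A reader could then carry an intermediate-risk conclusion over to flutter patients who have never had AF, the population the planned follow-on study would enrol, on the strength of inductions that came largely from patients in the highest class.

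**Working it through.** **1. Do the Group 3 criteria keep prior AF out?** The rhythm exclusion concerns what is characterised at the ablation, and the ablation criterion concerns what is ablated. Together they remove patients who show another arrhythmia at the procedure or who also need AF ablation. Neither refers to earlier documented AF. Group 2 has an explicit history exclusion, so the protocol has wording for the purpose but does not apply it here.

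**2. The plan's own sample size.** With pooled variance, two-sided 5% and 90% power:

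n = [1.96·√(2·p̄·q̄) + 1.2816·√(p₁q₁ + p₂q₂)]² / (p₁ − p₂)²

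For 1% v 30% (the rates given for the pulmonary vein group under Sample Size Calculation), p̄ = 0.155 and n = (1.003 + 0.601)² / 0.0841 = 30.6, so 31 per arm. This matches the 31 quoted for Experiment 3. At the 5% placebo bound that Experiment 3 states, the same formula gives 47, and 35 per arm has about 80% power. That is a separate matter, but it sets the baseline for step 5.

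**3. Inputs for the mixture.**
- f, the share of Group 3 with prior AF: not in the protocol; assumed 20% or 30%.
- h, inducibility with prior AF: 30% (the sponsor's planning rate under Sample Size Calculation), or 84% (the earlier uncontrolled study described in the background).
- b, inducibility without prior AF: assumed 5% or 10%, in line with the under-10% rate given for the SVT group in Experiment 4.

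Pooled rate = f·h + (1 − f)·b. Prior-AF share of inductions = f·h / pooled rate.

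| f | h | b | Pooled rate | Prior-AF share of inductions |
|---|---|---|---|---|
| 0.2 | 0.30 | 0.05 | 0.060 + 0.040 = 0.100 | 60% |
| 0.2 | 0.30 | 0.10 | 0.060 + 0.080 = 0.140 | 43% |
| 0.3 | 0.30 | 0.05 | 0.090 + 0.035 = 0.125 | 72% |
| 0.3 | 0.30 | 0.10 | 0.090 + 0.070 = 0.160 | 56% |
| 0.2 | 0.84 | 0.05 | 0.168 + 0.040 = 0.208 | 81% |
| 0.2 | 0.84 | 0.10 | 0.168 + 0.080 = 0.248 | 68% |
| 0.3 | 0.84 | 0.05 | 0.252 + 0.035 = 0.287 | 88% |
| 0.3 | 0.84 | 0.10 | 0.252 + 0.070 = 0.322 | 78% |

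If h = b = 30%, the prior-AF share of inductions equals f, that is 20-30%, and the pooled rate is 30% in both strata. Nothing is then distorted.

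**4. Events needed for significance.** At 35 per arm, two-sided Fisher significance needs 6 v 0 or 8 v 1. At h = 84%, 7 prior-AF patients in the isoprenaline arm give 7 × 0.84 = 5.9 expected events. At h = 30%, 6 expected events need 6 / 0.30 = 20 of the 35.

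**5. Size of the no-prior-AF stratum.** 35 × 0.8 = 28 and 35 × 0.7 = 24.5, so about 24-28 per arm. Power from the formula in step 2 is 63-70% for 30% v 5%, or 81-87% for 30% v 1%.

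**The case against.** The strongest reply is that Experiment 3 asks about patients after flutter ablation and answers exactly that. The intermediate label is attached to the procedure, and a mixed flutter population may well sit, as a group, between SVT and paroxysmal AF. The follow-on cohort is a separate future study and need not set this trial's eligibility. This stands as far as it goes: the randomised comparison is fair and has a clear population. It does not remove the overlap, because the same paragraph bases risk on rhythm history and puts known paroxysmal AF in another class.

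The second reply concerns size, and much of it stands. Under Sample Size Calculation the sponsor says that published rates above 80% do not match its clinical experience and plans on a far lower one, so 84% cannot be the only input. The 5-10% rate is borrowed from the low-risk group, whereas the protocol expects over 30% in the flutter group and cites up to 25% of flutter patients without documented AF developing it within 12 months. The prior-AF share has no source in the protocol.

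A reader might infer that a significant Experiment 3 result could come wholly from patients with known AF. The documents do not support that. Even at 84% the share of inductions is 68-88%, and at the planning rate 20 of 35 patients in the isoprenaline arm would need prior AF to supply six expected events. Nor does the near match between the mixture at 84% and the planned 30% count as evidence: it follows from three chosen inputs and disappears at the planning rate, where the pooled rate is 10-16%.

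Finally, a subgroup analysis may be in a SAP that is not shown. Its absence from the protocol is not the fault. The class definitions and the eligibility criteria are in the protocol, and they conflict there.

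**Conclusion.** The inconsistency stands on the text alone. Risk is defined by rhythm history and separate answers by risk are promised, yet Group 3 can contain patients who belong to the highest class. The consequence is limited to interpretation: the pooled Experiment 3 result is valid for flutter-ablation patients with or without prior AF, but cannot be attributed to an intermediate-risk or flutter-only class without further information.

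The size is not known. With 20-30% prior AF and 5-10% inducibility without it, prior-AF patients would supply about 43-72% of inductions at the 30% planning rate and 68-88% at the cited 84%. With equal inducibility of 30% in both strata there is no distortion. All of these are scenarios, since the protocol gives neither the prior-AF share nor separate rates within the flutter group.

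It would go too far to call the comparison biased or to say that prior AF must be excluded; the protocol supports neither.

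**What to change.** Keep the pooled Group 3 comparison as the primary test for Experiment 3. Prespecify that the result is also reported by documented prior AF, with an estimate and interval in each stratum. State in the protocol that Group 3 admits patients with or without prior AF, and describe the pooled result in those terms. Make an intermediate-risk or flutter-only statement only with the no-prior-AF estimate and its interval shown.

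This needs no new data, because previous arrhythmia episodes are already recorded at enrolment. The cost is precision: about 24-28 per arm without prior AF if 20-30% have it, with roughly 63-70% power for 30% v 5%. That stratum supports estimation, not a test at 90% power, and should not replace the primary analysis at the present sample size.

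Applying the Group 2 history exclusion to Group 3 is an option for the sponsor. It would keep all 35 per arm free of documented AF, at a cost in recruitment, but it is not a required change.
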